2.4.5.3 Deaths

The following summaries of deaths will be generated.

- Number (%) of patients who died by study period (on-study, on-treatment, post-study)
- Deaths in nonrandomized patients or randomized but not treated patients
- Treatment-emergent adverse events leading to death (death as an outcome on the adverse event case report form page as reported by the Investigator) by primary SOC, HLGT, HLT, and PT showing number (%) of patients sorted by internationally agreed SOC order, with HLGT, HLT, and PT presented in alphabetical order within each SOC.

2.4.5.4 Analyses of laboratory variables

Laboratory parameters will be grouped and summarized by biological function as described in Section 2.1.4.4.

The summary statistics (including number, mean, median, Q1, Q3, standard deviation, minimum and maximum) of all laboratory variables (central laboratory values, changes from baseline, and/or percent change from baseline [eg, lipid parameters, albumin, total protein, hemoglobin, hematocrit]) will be calculated for each applicable visit or study assessment (screening, baseline, postbaseline time point, last on-treatment value) by treatment group. Graphical presentations may be used to examine trends over time using mean (\pm SE) and/or mean change from baseline (\pm SE) at scheduled visits (eg, creatinine, eGFR).

The incidence of PCSAs (list provided in Appendix B) at any time during the treatment-emergent adverse event period will be summarized by biological function and treatment group whatever the baseline level and/or according to the following baseline status categories:

- Normal/missing
- Abnormal according to PCSA criterion or criteria

For creatinine, $\geq 50\%$ change from baseline will be provided in addition to the PCSA criteria defined, ie, $\geq 150 \mu\text{mol/L}$ (Adults), $\geq 30\%$ change from baseline, $\geq 50\%$ change from baseline, and $\geq 100\%$ change from baseline. For eGFR, $\geq 50\%$ decrease from baseline will be provided in

addition to the PCSA criteria defined, ie, <15 (end stage renal disease), ≥ 15 - <30 (severe decrease in GFR), ≥ 30 - <60 (moderate decrease in GFR), ≥ 60 - <90 (mild decrease in GFR), and $\geq 50\%$ decrease from baseline. For parameters for which no PCSA criteria are defined, similar tables using the normal range will be provided.

All measurements collected during the TEAE period, including values from unscheduled visits, will be considered for the PCSA summaries. These summaries will include patients in the safety population who have at least 1 assessment performed during the TEAE period. When a PCSA definition involves a change from baseline value, patients must also have a baseline value to be included in the summaries, and when required by the definition of the abnormality, patients must also have available laboratory normal ranges.

A listing of patients with at least 1 post-baseline PCSA (or out of normal range when no PCSA criterion is defined) will be provided which will display the entire patients' profile across time for all parameters belonging to the corresponding biological function. Individual data listings will include the following flags when applicable:

- Baseline values will be flagged "B".
- Normal laboratory ranges, available for most laboratory parameters, will be identified as ULN and lower limit of normal (LLN). Baseline, last on-treatment value, and individual data will be flagged "L" if the value is below the LLN and will be flagged "H" if it is above the ULN.
- Laboratory PCSA criteria will be used for the corresponding laboratory parameters. Values reaching a PCSA limit will be flagged (+, ++, -, or -- depending upon the direction and level of the abnormality). Flags for WBC and differential counts will be determined using data expressed in international units.

For parameters whose PCSA criteria are multiples of the ULN, the parameter's value will also be expressed as a multiple of the ULN in the individual data provided.

Drug-induced liver injury

The liver function tests, namely AST, ALT, alkaline phosphatase, and total bilirubin, are used to assess possible drug-induced liver toxicity. The proportion of patients with PCSA values at any postbaseline visit by baseline status will be displayed by treatment group for each parameter. The proportion of patients with PCSA values at any postbaseline visit will also be displayed by duration of exposure (see Section 2.4.3.1) for each treatment group (only if a tabulation summary is necessary).

Listing of possible Hy's law cases identified by treatment group (eg, patients with any elevated ALT > 3 x ULN, and associated with an increase in bilirubin ≥ 2 x ULN) with ALT, AST, alkaline phosphatase, total bilirubin, and the following complementary parameters (if available): conjugated bilirubin and prothrombin time/international normalized ratio, creatine phosphokinase, serum creatinine, complete blood count, anti-HAV IgM, anti-HBc IgM, anti-HCV and HCV RNA, anti-CMV IgM and anti-HEV IgM antibodies, auto-antibodies: anti-nuclear, anti-DNA, anti-smooth muscle, Epstein-Barr virus, herpes viruses, and anti-LKM.

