### 7.1 INCLUSION CRITERIA

Patients meeting all of the following inclusion criteria will be screened:

- I 01. Patients with T2D (drug-naïve or on antidiabetic therapy) and documented severe renal insufficiency - CKD4 - defined by an eGFR equation (based on the 4 variable modification of diet in renal disease [MDRD] equation) of  $\geq 15$  and  $< 30$  mL/min/1.73 m^2.
- I 02. Signed written informed consent to participate in the study in accordance with local regulations.

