### **7.2.2 Exclusion criteria related to the diabetes or CKD history and treatment**

- E 13. Type 1 diabetes mellitus.
- E 14. HbA1c <7% or >11% measured by the central laboratory at Screening.
- E 15. Oral antidiabetic agent or insulin use where the dose was not stable for 8 weeks before randomization (ie, oral agents changed during past 8 weeks or total daily basal insulin dose increased or decreased by more than 20% during the past 4 weeks).
- E 16. Use of a selective SGLT2 inhibitor (eg, canagliflozin, dapagliflozin, or empagliflozin) within 12 months prior to the trial.
- E 17. History of DKA or nonketotic hyperosmolar coma within 12 weeks prior to the Screening Visit.
- E 18. History of severe hypoglycemia that resulted in unconsciousness, coma, or hospitalization within 6 months prior to the Screening Visit.
- E 19. CKD stage 5: defined as chronic dialysis or eGFR < 15.
- E 20. Reversible causes of renal failure such as obstruction within 6 months of Screening.

E 21. Renal disease that required treatment with immunosuppressive therapy within the last 12 months, or renal transplant or initiation of chronic dialysis within 4 weeks prior to the Screening Visit or expected to occur during the study duration.

E 22. History of hereditary glucose galactose malabsorption or primary renal glucosuria.

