2.4.5 Analyses of safety data

The summary of safety results will be presented by treatment group. The safety data will be summarized for the 26-week core treatment period and the 52-week entire treatment period separately, unless otherwise specified.

The “observation period” defined in [Section 2.1.4](#) is applicable in all safety analyses for the classification of AEs, determination of treatment-emergent PCSA values and the last on-treatment value for the laboratory, vital sign and ECG.

General common rules

All safety analyses will be performed on the safety population as defined in [Section 2.3.2](#), unless otherwise specified, using the following common rules:

- Safety data in patients who do not belong to the safety population (eg, exposed but not randomized) will be listed separately
- The baseline value (with the exception of serum creatinine and eGFR) is defined as the last available value before the first dose of double-blind IMP. For serum creatinine and eGFR, the baseline value is defined as the average of all values before the first dose of double-blind IMP.
- PCSA values are defined as abnormal values considered medically important by the Sponsor according to predefined criteria/thresholds based on literature review and defined by the Sponsor for clinical laboratory tests, vital signs, and ECG ([Appendix B](#))
- PCSA criteria will determine which patients had at least 1 PCSA during the treatment-emergent adverse event period, taking into account all evaluations performed during the treatment-emergent adverse event period, including nonscheduled or repeated evaluations.

The number of all such patients will be the numerator for the treatment-emergent PCSA percentage.

- The treatment-emergent PCSA denominator by group for a given parameter will be based on the number of patients assessed for that given parameter in the treatment-emergent adverse event period by treatment group on the safety population.
- For laboratory parameters cited in the protocol as efficacy endpoints (including HbA1c and plasma glucose etc), PCSA summaries will not be provided. These parameters will be summarized in efficacy [Section 2.4.4](#).

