2.5 DATA HANDLING CONVENTIONS**2.5.1 General conventions**

The following formulas will be used for computation of parameters.

HbA1c

The formula to convert HbA1c from Diabetes Control and Complications Trial (DCCT) aligned value to International Federation of Clinical Chemistry and Laboratory Medicine (IFCC) standardized value is,

$$\text{IFCC-HbA1c (mmol/mol)} = [\text{DCCT-HbA1c (\%)} - 2.15] \times 10.929.$$

Renal function formulas

The estimated GFR (mL/min/1.73 m²) will be calculated using the 4 variable Modification of Diet in Renal Disease (MDRD) formula:

$$\text{Standard unit: eGFR (mL/min/1.73 m}^2\text{)} = 175 \times [\text{Serum Creatinine } (\mu\text{mol/L})/88.4]^{-1.154} \times \text{Age (year)}^{-0.203} \times 1.212 \text{ (if Black)} \times 0.742 \text{ (if female)}$$

$$\text{Conventional unit: eGFR (mL/min/1.73 m}^2\text{)} = 175 \times \text{Serum Creatinine (mg/dL)}^{-1.154} \times \text{Age (year)}^{-0.203} \times 1.212 \text{ (if Black)} \times 0.742 \text{ (if Female)}$$

UACR

$$\text{Standard unit: UACR (mg/g)} = \text{Urine Albumin (mg/dL)} / [\text{Urine Creatinine (mmol/L)} \times 11.31] \times 1000$$

$$\text{Conventional unit: UACR (mg/g)} = \text{Urine Albumin (mg/dL)} / \text{Urine Creatinine (mg/dL)} \times 1000$$

UGCR

$$\text{Standard unit: UGCR} = \text{Urine Glucose (mmol/L)} / \text{Urine Creatinine (mmol/L)}$$

$$\text{Conventional unit: UGCR} = \text{Urine Glucose (mg/dL)} / \text{Urine Creatinine (mg/dL)}$$

Calculation of LDL-C

When TG is lower than or equal to 4.52 mmol/L (400 mg/dL), LDL-C is calculated using the Friedewald equation as:

- in standard unit (mmol/L), $\text{TC} - \text{HDL-C} - \text{TG}/2.17$;
- in conventional unit (mg/dL), $\text{TC} - \text{HDL-C} - \text{TG}/5$.

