CLcr (mL/min) (Estimated creatinine clearance based on the Cockcroft -Gault equation)	<15 (end stage renal disease) ≥15 - <30 (severe decrease in GFR) ≥30 - < 60 (moderate decrease in GFR) ≥60 - <90 (mild decrease in GFR) ≥ 90 (normal GFR)	FDA draft Guidance 2010 Pharmacokinetics in patients with impaired renal function-study design, data analysis, and impact on dosing and labeling
eGFR (mL/min/1.73m2) (Estimate of GFR based on an MDRD equation)	<15 (end stage renal disease) ≥15 - <30 (severe decrease in GFR) ≥30 - < 60 (moderate decrease in GFR) ≥60 - <90 (mild decrease in GFR) ≥ 90 (normal GFR)	FDA draft Guidance 2010 Pharmacokinetics in patients with impaired renal function-study design, data analysis, and impact on dosing and labeling
Creatinine	≥150 µmol/L (Adults) ≥30% change from baseline ≥100% change from baseline	Benichou C., 1994.
Uric Acid Hyperuricemia Hypouricemia	>408 µmol/L <120 µmol/L	Harrison- Principles of internal Medicine 17 th Ed., 2008.
Blood Urea Nitrogen	≥17 mmol/L	
Chloride	<80 mmol/L >115 mmol/L	
Sodium	≤129 mmol/L ≥160 mmol/L	
Potassium	<3 mmol/L ≥5.5 mmol/L	FDA Feb 2005.
Total Cholesterol	≥7.74 mmol/L	Threshold for therapeutic intervention.
Triglycerides	≥4.6 mmol/L	Threshold for therapeutic intervention.
Lipasemia	≥3 ULN	
Amylasemia	≥3 ULN	

CRITERIA for POTENTIALLY CLINICALLY SIGNIFICANT ABNORMALITIES
for phase 2/3 studies (oncology excepted)
(From BTD-009536 May 21, 2014)

Parameter	PCSA	Comments
Glucose		
Hypoglycaemia	≤3.9 mmol/L and <LLN	ADA May 2005.
Hyperglycaemia	≥11.1 mmol/L (unfasted); ≥7 mmol/L (fasted)	ADA Jan 2008.
HbA1c	>8%	
Albumin	≤25 g/L	
CRP	>2 ULN or >10 mg/L (if ULN not provided)	FDA Sept 2005.
Hematology		
WBC	<3.0 Giga/L (Non-Black); <2.0 Giga/L (Black) ≥16.0 Giga/L	Increase in WBC: not relevant. To be interpreted only if no differential count available.
Lymphocytes	>4.0 Giga/L	
Neutrophils	<1.5 Giga/L (Non-Black); <1.0 Giga/L (Black)	International Consensus meeting on drug-induced blood cytopenias, 1991. FDA criteria.
Monocytes	>0.7 Giga/L	
Basophils	>0.1 Giga/L	
Eosinophils	>0.5 Giga/L or >ULN (if ULN ≥0.5 Giga/L)	Harrison- Principles of internal Medicine 17 th Ed., 2008.
Hemoglobin	≤115 g/L (Male); ≤95 g/L (Female) ≥185 g/L (Male); ≥165 g/L (Female) Decrease from Baseline ≥20 g/L	Criteria based upon decrease from baseline are more relevant than based on absolute value. Other categories for decrease from baseline can be used (≥30 g/L, ≥40 g/L, ≥50 g/L).

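### Two of the nine renal PCSA rows are met at entry by nearly every eligible patient, and a third lists eGFR values above the entry range as a moderate decrease

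*SAP*

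**What the plan says.** SAP 2.4.5.4 states that "The incidence of PCSAs (list provided in Appendix B) at any time during the treatment-emergent adverse event period will be summarized by biological function". For creatinine and eGFR it names nine rows:

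- Creatinine: ≥150 µmol/L, and changes from baseline of ≥30%, ≥50% and ≥100%.
- eGFR: <15; 15 to <30 (labelled a severe decrease); 30 to <60 (moderate decrease); 60 to <90 (mild decrease); and a ≥50% decrease from baseline.

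The two ≥50% rows were added for this study. The others come from SAP Appendix B, a general phase 2/3 list. There the eGFR entry is described as "Estimate of GFR based on an MDRD equation" and the relative creatinine criteria as "≥30% change from baseline ≥100% change from baseline".

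SAP 2.4.5 gives the counting rule: "PCSA criteria will determine which patients had at least 1 PCSA during the treatment-emergent adverse event period". Unscheduled and repeat values count, and the result is named the treatment-emergent PCSA percentage. A value need not be new or worse than baseline. Under 2.4.5.4 the table may be shown overall and/or split by baseline status. The same section asks for a listing, with full profiles, of all patients who have at least one post-baseline PCSA.

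Protocol 7.1 requires CKD stage 4 "defined by an eGFR equation (based on the 4 variable modification of diet in renal disease [MDRD] equation) of" at least 15 and below 30 mL/min/1.73 m². Protocol 7.2.2 excludes "CKD stage 5: defined as chronic dialysis or eGFR < 15".

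**The concern.** A PCSA is meant to pick out values that matter medically and arose on treatment. Here the entry criterion itself places patients inside two of the classes, so those rows restate eligibility. The row for eGFR 30 to <60 can be entered only by a value above the patient's screening eGFR, yet its label speaks of a decrease. An arm with more eGFR recovery would show more entries under that label.

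At stake is how readable the renal safety tables are in a population where renal safety is closely watched. The listing has the same fault: if nearly everyone qualifies, it no longer isolates patients of concern.

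**Working it through.** The plan states no expected PCSA incidence, so there is no figure to reproduce. The check asks which rows an eligible patient meets before dosing.

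**1. Formula.** SAP 2.5.1 says eGFR "will be calculated using the 4 variable Modification of Diet in Renal Disease (MDRD) formula": 175 × (creatinine/88.4)^−1.154 × age^−0.203, × 1.212 if Black, × 0.742 if female. Solved for creatinine in µmol/L:

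creatinine = 88.4 × (175 × age^−0.203 × race × sex / eGFR)^(1/1.154)

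Creatinine is lowest at the top of the entry range, so eGFR 30 is the limiting case. For a non-Black woman aged 80, 80^−0.203 = 0.4108; 175 × 0.4108 × 0.742 / 30 = 1.778; 1.778^(1/1.154) = 1.647; × 88.4 = 145.6.

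| Creatinine (µmol/L) at eGFR 30 | Age 40 | Age 65 | Age 90 |
|---|---|---|---|
| Non-Black men | 213.0 | 195.5 | 184.7 |
| Black men | 251.6 | 231.0 | 218.1 |
| Black women | 194.3 | 178.4 | 168.4 |
| Non-Black women | 164.5 | 151.0 | 142.6 |

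All eligible men and all Black women are above 150 at screening. The only exceptions are non-Black women older than about 67.5 years with eGFR near the upper limit: above 29.8 at age 70, 29.0 at 80 and 28.3 at 90. This step uses only the documents.

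**2. On-treatment incidence with no drug effect.** This needs assumptions that the documents do not give: mean age 67 (SD 9), or 75 (SD 7) in an extreme case; 30–70% women; 0–5% Black; within-patient creatinine CV 5–10%. Screening eGFR is held to 15 to <30. There are 10 scheduled post-baseline values, as in the flow chart (Weeks 1, 2, 3, 4, 8, 12, 18, 26, 39 and 52). Ranges are over the scenarios simulated.

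| Row | At baseline | At least once on treatment |
|---|---|---|
| Creatinine ≥150 µmol/L | 92–99% | 98–99.8% |
| eGFR 15 to <30 | 88–95% | 98–99% |
| eGFR 30 to <60 | 3–11% (eGFR ≥30) | 18–48% |
| eGFR 60 or more | not tabulated | about 0% |
| eGFR <15 | 0.6–3% | 4–20% |
| Creatinine ≥30% above baseline | not applicable | 0–10% |
| Creatinine ≥50% above baseline | not applicable | 0–0.3% |

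Baseline is not confined to 15 to <30 because SAP 2.1.1 averages all pre-dose values, while eligibility rests on screening.

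**3. Direction of the 30 to <60 row.** Every patient screened below 30. Of those counted in this row, 78–81% also had an averaged baseline below 30, so their entry is a rise. For the remaining fifth or so, the averaged baseline was already ≥30 and the entry is not clearly a rise.

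**4. Baseline-status split.** For creatinine ≥150, about 1 to 7 of 92 patients per arm would fall in the normal/missing stratum. The split is also optional as worded.

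**5. Rows that work.** With an exponent of 1.154, creatinine rises of 30%, 50% and 100% correspond to eGFR falls of 1 − 1.3^−1.154 = 26%, 1 − 1.5^−1.154 = 37% and 1 − 2^−1.154 = 55%. These rows do not saturate. Nor does eGFR <15, which is excluded at entry.

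**6. Two SAP sections side by side.** Section 2.4.5 says no PCSA summaries will be given for laboratory parameters that the protocol cites as efficacy endpoints. Change in eGFR is such an endpoint (Protocol 9.1.3; SAP 2.1.3.3), yet 2.4.5.4 prescribes eGFR PCSA rows.

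**The case against.** The strongest reply is that little depends on these rows. Only two of nine saturate, and five are informative: three relative creatinine rows, eGFR <15 and eGFR ≥50% decrease. The sponsor had already adapted the list by adding the ≥50% rows. The eGFR labels come from an absolute classification relative to normal function, and the change row is separately worded as a decrease from baseline. The 60 to <90 row would be practically empty. Safety analysis is descriptive, and nothing ranks PCSA rows first for renal safety. Protocol 11.4.3.5 already permits shift tables. Removing prespecified rows after the first-step analysis was reported for topline results (SAP 1.6) also needs a reason.

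All of that stands, and it limits the point to presentation. It does not remove it. A class label that is harmless in a baseline table misleads in one headed as treatment-emergent abnormality, and the baseline split rescues almost nobody.

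A reader might infer that the creatinine and eGFR PCSA rows are uninformative as a whole, or that the plan would miss or bias a renal signal. The documents do not support either. SAP 2.1.4.2 defines renal events of special interest (sustained ≥50% eGFR decrease, sustained eGFR <15, dialysis, transplant, renal death). SAP 2.4.4.3 gives counts and Kaplan-Meier plots for ESRD and for >50% eGFR decline. SAP 2.4.5.2 tabulates acute renal failure, and 2.4.5.4 itself summarises change from baseline by visit.

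**Conclusion.** The point holds for three rows. Creatinine ≥150 µmol/L and eGFR 15 to <30 describe the entry criterion and would read about 98–100% in every arm, so they cannot separate treatments. The eGFR 30 to <60 row reports values above the screening eGFR as a PCSA labelled a decrease; usually these are rises.

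The creatinine limits by age, sex and race follow from the SAP formula alone. The percentages rest on the assumed age, sex and race mix, creatinine CV and absence of drug effect; the near-saturation of the two rows persists across all the ranges tried.

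The consequence is misleading descriptive tables and a renal listing that takes in nearly the whole safety population. No efficacy conclusion is affected, and the renal safety signal is not lost. The conflict between SAP 2.4.5 and 2.4.5.4 on eGFR is a separate, smaller inconsistency.

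**What to change.** In SAP 2.4.5.4 and Appendix B, for this study:

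1. Do not report creatinine ≥150 µmol/L or the eGFR classes 15 to <30, 30 to <60 and 60 to <90 as treatment-emergent PCSA rows.
2. Keep the ≥30%, ≥50% and ≥100% creatinine rows, stating that they count increases; eGFR <15 among patients with baseline ≥15; and eGFR ≥50% decrease from baseline. A row for eGFR ≥30% decrease is optional.
3. Show the eGFR classes only as a baseline-by-worst-value shift table.
4. Base the renal PCSA listing on the retained rows.
5. State in 2.4.5 that eGFR is an exception to the rule on efficacy-endpoint laboratory parameters, or otherwise reconcile it with 2.4.5.4.

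The cost is SAP wording and table shells; no new data are needed. It departs from the sponsor's standard list after topline results, so the reason, which rests on the eligibility criterion and the eGFR formula and not on any result, should be recorded in the SAP change table.

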2.4.5.5 Analyses of vital sign variables

The summary statistics (including number, mean, median, Q1, Q3, standard deviation, minimum and maximum) of heart rate, temperature and respiratory rate (observed values or mean of observed values, and changes from baseline) will be calculated for each applicable visit or study assessment (baseline, post-baseline time points, last on-treatment value) by treatment group.

The incidence of PCSAs at any time during the TEAE period will be summarized by treatment group for SBP, DBP and HR. All measurements collected during the TEAE period, including values from unscheduled visits, will be considered for the PCSA summaries. The summaries will include patients in the safety population who have at least 1 assessment performed during the TEAE period. When a PCSA definition involves a change from baseline value, patients must also have a baseline value to be included in the summaries.

A listing of patients with at least 1 post-baseline PCSA will be provided and will display the patient's profile over time of all vital sign parameters. Individual data listings will include the following flags:

- Baseline values will be flagged "B",
- Parameter values reaching a PCSA limit will be flagged (+, or - depending of the direction).

2.4.5.6 Analyses of electrocardiogram variables

Shift tables will be provided to present ECG status according to baseline status (Normal/Missing, Abnormal) for each treatment group during the TEAE period. Supportive listings of patients with abnormal ECG status at any post-baseline visit will be provided.

2.4.5.7 Analyses of physical examination variables

Shift tables will be provided to present physical examination findings by body system according to baseline status (Normal/Missing, Abnormal) for each treatment group during the TEAE period. Supportive listings of patients with abnormal findings at any post-baseline visit will be provided.

